## 6.5. CONCOMTANT TREATMENT

All concomitant medication used throughout the treatment period and safety follow-up period (30, 60 and 90 days after the last dose of the study drug) should be recorded starting from the signature of the ICF by the subjects, which should include the dose, regimen, route, indications, starting date and end date of the concomitant drug.

## 6.5.1. Prohibited Medications/Vaccines

The following medications and procedures are prohibited during the study:

- use of strong CYP3A4 inhibitors and inducers is prohibited during the study (Please refer to Section 错误!未找到引用源。
- Do not use any anti-tumor drugs other than the study drug (irrespective of those approved by the Health Authority or investigational treatment), including but not limited to chemotherapy, radiotherapy, immunotherapy, bio-targeted therapy, hepatic intervention, local therapy and traditional Chinese medicines with anti-hepatocellular carcinoma indication.

- Palliative local therapy (including surgery and radiation therapy) to extrahepatic non-target lesions may be allowed.

- Immunosuppressive agents, including but not limited to systemic corticosteroids, etc. (the dose higher than 10 mg/day prednisone or equivalent dose), with the exception of special circumstances requiring such agents for the treatment of an AE, in which the investigator must discuss with the sponsor's medical monitor.
- The use of live vaccines should be prohibited during the study period.
- For Phase Ib, prophylactic medications, such as prophylactic anti-emetic, prophylactic colony-stimulating factor, erythropoietin etc., are not permitted during the DLT observation period (D1 to D21 of Cl). Drugs or treatments that correct hematologic toxicity are not allowed.

## 6.5.2. Permitted Treatment

The permitted treatments for this study include:

- After discussion and consultation with the medical monitor, the investigator can perform supportive treatment (e.g. local radiotherapy against pain (extra-hepatic non-target lesions only)), or thoracic puncture and drainage to relieve the subject's symptoms).
- Bisphosphonates indicated for bone metastases are permitted during the study period.
- Local, ocular, intraarticular, intranasal and inhaled glucocorticoids therapies (with extremely low systemic absorption) in subjects are also acceptable; ≤ 10 mg/day of prednisone or equivalent dose of the similar drugs as the adrenal alternative therapy are also acceptable; short-term (<3 weeks) use of glucocorticoids for prophylactic treatment (e.g. to prevent allergy to contrast medium) or for the treatment of non-autoimmune diseases (e.g., delayed type hypersensitivity caused by contact with allergen) is also allowable.

## 6.6. SPECIAL PRECAUTIONS

Subjects should be closely observed and monitored during the administration of CS1001 up to 30 minutes after completion of the infusion.

If a grade 2 or higher hypersensitivity reaction, inflammatory reaction or infusion-related reaction occurs, the CS1001 infusion will be discontinued. Recommendations for treatment of infusion-related reactions and severe hypersensitivity reactions according to NCI are presented in sections错误!未找到引用源。 and错误!未找到引用源。 respectively.

## 6.6.1. Infusion-Related Reaction

Infusion-related reaction symptoms include fever, chills, nausea, itching, angioedema,

hypotension, headache, bronchospasm, urticaria, rash, vomiting, myalgia, dizziness or high blood pressure. Severe reactions include acute respiratory distress syndrome, myocardial infarction, ventricular fibrillation and cardiogenic shock. The subjects should be closely monitored for such reactions. Please refer to Table 9 for treatment adjustments for infusion-related reactions caused by administration of CS1001.

The site must have conditions for the treatment of serious infusion-related reactions, such as immediate access to the intensive care unit (ICU) or the equal environment and availability of appropriate treatment (including adrenaline, corticosteroids, intravenous antihistamines, bronchodilators and oxygen). In the event of an infusion-related allergic reaction or an allergic

reaction of  $\geq 2$  level, the CS1001 infusion will be stopped.

In the event of hypersensitive reactions, the best available medical treatment must be taken for these subjects. Based on the guidelines for emergency treatment of allergic reactions published by Resuscitation Association Working Group (UK), it is recommended that subjects should immediately report any delayed response to the investigator.

 Table 9:Treatment adjustments for infusion-related reaction symptoms after administration of CS1001

NCI-CTCAE Classification	Treatment Adjustment for CS1001			
Level 1 - Mild Mild and transient reactions; no need to interrupt infusion; and no intervention required.	When the infusion rate of CS1001 decreases by 50%, it is necessary to closely monitor any worsening reaction until the reaction disappears. Medical treatment can be given on demand.			
Level 2 - Moderate The need of treatment or infusion interruption, and timely relief after symptomatic treatment (e.g., antihistamines, NSAIDs, anesthetics, intravenous fluids, etc.); and the need of prophylactic treatment with treatment time $\leq 24$ hours.	CS1001 infusion should be suspended. Once the infusion-related reaction disappears or the severity drops to level 1 or below, the infusion may be restarted at a rate reduced to 50% of the previous rate, and any worsening reaction should be closely monitored. Appropriate medical management strategies should be established based on the following text.			
Level 3 or Level 4 - Severe or life-threatening Level 3: The delay of symptom relief (e.g., symptomatic administration and/or the failure of timely relief after transient interruption of the infusion); the symptomatic relapse after initial improvement; and hospitalization or clinical consequences (e.g., kidney damage, pulmonary infiltration, etc.) due to clinical sequelae. Level 4: life-threatening; and the need of emergency intervention (e.g., the need of ventilator support, etc.).	The CS1001 infusion should be discontinued immediately and the infusion tube connected to the subject should be disconnected. Whether to continue the study treatment will be determined by the investigator. Appropriate medical management strategies should be established, as described below; The subject should immediately withdraw from CS1001 treatment group and should not receive additional CS1001 treatment. Appropriate medical management strategies should be established based on the following text.			

NCI-CTCAE = National Cancer Institute Common Terminology Criteria for Adverse Events; NSAIDs = Non-Steroidal Anti-Inflammatory Drugs.

Once the infusion rate of CS1001 is reduced by 50% or the infusion is suspended due to infusion-related reactions, the reduced infusion rate must be maintained at all subsequent infusions. If the subject occurs the infusion-related reaction ( $\geq$  level 2) for the second time at a slower infusion rate, the infusion should be discontinued, and the subject should withdraw from CS1001 treatment group.

**Infusion Reactions of CTCAE Level 1 or Level 2:** Appropriate medical treatment strategies should be established according to the reaction type. It includes but is not limited to antihistamines (e.g., diphenhydramine or equivalent drugs), antipyretic agents (e.g., paracetamol or equivalent drugs), oral or intravenous corticosteroids on demand, epinephrine, bronchodilators and oxygen. Bedside monitoring must be continued until symptom relief is achieved. In the subsequent dosing period, the subject will receive prophylactic oral antihistamines (e.g., diphenhydramine or

equivalent drugs) and antipyretic agents (e.g., paracetamol or equivalent drugs) at least 30 minutes prior to infusion and will be closely monitored for infusion-related clinical signs and symptoms.

**Infusion Reactions of CTCAE Level 3 or 4:** The infusion should be discontinued immediately. Appropriate medical management strategies should be established immediately according to severity and type of the reaction. It includes but is not limited to oral or intravenous antihistamines, antipyretic agents, corticosteroids, epinephrine, bronchodilators and oxygen.

Whenever the subject occurs an infusion-related reaction of Level 4, CS1001 must be discontinued.

If an infusion-related reaction of Level 3 occurs, whether to continue the study treatment will be determined by the investigator after consulting with the sponsor. If it is decided to continue the treatment, the infusion time of CS1001 should be at least 1 hour for **the next dosing period**. Prophylactic antihistamines (e.g., diphenhydramine 50 mg or equivalent drugs) and antipyretic agents (e.g., paracetamol, non-steroidal anti-inflammatory drugs (NSAIDs) or equivalent drugs) will be given within 30 to 60 minutes prior to infusion. The subject will be closely monitored for infusion-related clinical signs and symptoms.

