## 6.4.4. CS1001 Permanent Discontinuation

Subjects will be required to permanently discontinued CS1001 for the following drug relatedadverse events:

- Any Grade 2 CS1001-related uveitis, eye pain or blurred vision that does not respond to topical therapy and does not improve to Grade 1 severity within the re-treatment period OR requires systemic treatment.
- ≥ Grade 3 infusion-related reaction during or after CS1001 infusion see Section 错误!未找到引用源。
- Grade 3-4 severe pneumonitis
- Any Grade 3 non-skin, drug-related adverse event lasting > 7 days, with the following exceptions:
  - Grade 3 drug-related uveitis, pneumonitis, bronchospasm, hypersensitivity reaction, or infusion reaction of any duration requires discontinuation.
  - Grade 3 drug-related endocrinopathies adequately controlled with only physiologic hormone replacement do not require discontinuation.
  - Grade 3 drug-related laboratory abnormalities do not require treatment discontinuation except:
    - Grade 3 drug-related thrombocytopenia >7 days or serious uncontrollable bleeding event requires discontinuation;
    - any drug-related liver function test (LFT) abnormalities that meet the following criteria requires discontinuation:
      - AST or ALT > 5-10  $\times$  ULN for 2 weeks
      - AST or ALT  $> 10 \times ULN$
      - Total bilirubin  $> 5 \times ULN$
      - Concurrent AST or ALT >  $3 \times$  ULN and total bilirubin >  $2 \times$  ULN
- Any Grade 4 drug-related adverse event or laboratory abnormality, except for the following events which do not require discontinuation:
  - Grad4 neutropenia  $\leq$  7 days

- Grade 4 lymphopenia or leukopenia
- Isolated Grade 4 electrolyte imbalances/abnormalities that are not associated with clinical sequelae and are corrected with supplementation/appropriate management within 72 hours of their onset.
- Grade 4 drug-related endocrinopathy adverse events, such as adrenal insufficiency, ACTH deficiency, hyper- or hypothyroidism, or glucose intolerance, which resolve or are adequately controlled with physiologic hormone replacement (corticosteroids, thyroid hormones) or glucose-controlling agents, respectively, may not require discontinuation after discussion with and approval from the sponsor Medical Monitor.
- Any event that leads to delay in dosing lasting > 9 weeks from the scheduled dosing requires discontinuation, with the following exceptions:

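### After a Grade 3 infusion-related reaction, Protocol 6.4.4 requires CS1001 to be stopped for good, while 6.6.1 allows it to be given again after the sponsor has been consulted

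*Protocol*

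**What the plan says.** **Protocol 6.4.4** opens its list with a requirement: "Subjects will be required to permanently discontinued CS1001 for the following drug relatedadverse events". One listed event, at that grade or above, is a "Grade 3 infusion-related reaction during or after CS1001 infusion". A later bullet repeats the rule without condition: "Grade 3 drug-related uveitis, pneumonitis, bronchospasm, hypersensitivity reaction, or infusion reaction of any duration requires discontinuation".

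**Protocol 6.6.1**, in the text on Level 3 and 4 reactions, requires CS1001 to be stopped after Level 4. For Level 3 it says that when an "infusion-related reaction of Level 3 occurs, whether to continue the study treatment will be determined by the investigator after consulting with the sponsor". It continues: "If it is decided to continue the treatment, the infusion time of CS1001 should be at least 1 hour". This applies to the next dosing period, with antihistamine and antipyretic premedication.

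**Table 9 in 6.6.1**, for Levels 3 and 4, contains both instructions: "Whether to continue the study treatment will be determined by the investigator" and "The subject should immediately withdraw from CS1001 treatment group and should not receive additional CS1001 treatment".

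Two further rules bear on infusion speed. Protocol 6.2.2 gives the normal CS1001 infusion time as 60 to 120 minutes and permits a longer one after a reaction. Protocol 6.6.1 says that once the rate has been halved or the infusion suspended because of a reaction, "the reduced infusion rate must be maintained at all subsequent infusions".

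**The concern.** A subject with a severe infusion reaction is barred from further CS1001 under one section and may receive it under another. With 20 sites planned, two investigators could act in opposite ways on the same event and each cite the protocol. The status of a re-dose also depends on the section: under 6.4.4 it departs from a stated rule and has to be documented, while under 6.6.1 it is compliant.

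The stake is mainly participant safety, because 6.6.1 itself counts acute respiratory distress syndrome, myocardial infarction and cardiogenic shock among severe reactions. A smaller stake is reporting. Discontinuation is part of the Phase II tolerance endpoint (Protocol 3.2). SAP 3.3.1 counts subjects who ended each drug, and SAP 3.5.3 summarizes events that led to discontinuation. Those counts would depend partly on which section a site followed.

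**Working it through.** **1. Is it the same event?** Table 9 classifies reactions by NCI-CTCAE, and 6.4 grades adverse events by the same system. Level 3 in 6.6.1 is therefore Grade 3 in 6.4.4.

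**2. Is it the same drug?** In the Level 3 paragraph, study treatment cannot mean BLU-554 alone, because the next sentence sets the CS1001 infusion time and premedication.

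**3. The two rules side by side**

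| Reaction | 6.4.4 | 6.6.1 text |
|---|---|---|
| Grade/Level 3 | CS1001 permanently discontinued | Investigator decides after consulting the sponsor |
| Grade/Level 4 | CS1001 permanently discontinued | CS1001 must stop |

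The rules differ only at Grade 3, and there they conflict directly.

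**4. Does other text settle it?**
- The first 6.4.4 bullet carries a cross-reference whose target is unreadable. The second bullet has none and is unconditional.
- Where 6.4.4 wants a sponsor-approved exception it writes one (Grade 4 endocrinopathy, delays beyond 9 weeks). It writes none for infusion reactions.
- Protocol 6.6 stops the infusion from Grade 2 upward but does not say whether later doses may be given.
- Protocol 6.6.2 covers generalized allergic or anaphylactoid reactions, not every Grade 3 infusion reaction.
- In the text of Table 9 the boundary between the Level 3 and Level 4 cells cannot be relied on. The point rests on 6.4.4 against the 6.6.1 text.

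**5. What does the one-hour condition add?** One hour is 60 minutes, and the normal minimum in 6.2.2 is 60 minutes: 60 − 60 = 0 minutes added. Section 6.2.2 is the right source for Phase II, because footnote p of the Phase II schedule (Table 3) states the 60 to 120 minutes for Cycle 1 only.

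**6. How often might it arise?** Protocol 2.4.1.2 reports no infusion-related events in 29 CS1001 monotherapy subjects. Exact two-sided 95% upper limit: 1 − 0.025^(1/29) = 0.119. The documents give no Grade 3 rate for the combination, so the rates below are assumptions. Chance of at least one case = 1 − (1 − p)^n:

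| Assumed rate p | n = 25 (IHC+ only) | n = 40 (planned Phase II) | n = 55 (40 IHC+ and 15 IHC−) |
|---|---|---|---|
| 0.5% | 12% | 18% | 24% |
| 1% | 22% | 33% | 42% |
| 3% | 53% | 70% | 81% |

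**7. Effect on the reported proportion.** One subject classified differently moves it by 1/40 = 2.5 points, or 1/25 = 4.0 points.

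**The case against.** The strongest defence is that the protocol already contains the risk. Section 6.4 calls its rules guidelines, says that discontinuation should also reflect the clinical circumstance, and allows deviations that are documented and communicated. Section 6.6.1 requires sponsor consultation before re-dosing after Level 3. The sponsor should therefore know of every such case, which limits how far sites can diverge. The specific premedication and timing given for Level 3 also suggest that re-dosing may have been intended, with 6.6.1 as the detailed rule to which the unreadable cross-reference points.

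Much of this stands, and it is why the point is minor. It does not reconcile the text. Section 5.6.1 names 6.4.4 as a source of protocol-specified discontinuation criteria, so 6.4.4 is more than advice. Allowing a documented deviation from a rule is also different from a second rule under which the same act is no deviation. If re-dosing was intended, the unconditional second bullet of 6.4.4 is wrong as written.

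A reader might also infer that CS1001 can be given two to four times as fast after a Level 3 reaction as after a milder one, by setting 60 minutes against the 120 to 240 minutes that a halved rate implies. The documents do not support that as a general statement. One hour is a floor, not a cap, and 6.2.2 permits a longer infusion. The reduced-rate rule in 6.6.1 is not confined to milder reactions: it applies once an infusion has been slowed or suspended because of a reaction. Table 9 describes Level 3 partly by failed relief after a brief interruption and by relapse after improvement, so some Level 3 subjects may already fall under that rule. A second reaction of Level 2 or above at the slower rate also leads to withdrawal from CS1001.

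**Conclusion.** The inconsistency is real: for a Grade 3 infusion-related reaction, 6.4.4 requires permanent discontinuation of CS1001 and 6.6.1 allows re-dosing after sponsor consultation. No readable text reconciles them. The one-hour condition in 6.6.1 does not by itself require slowing; nothing stronger about infusion speed is claimed.

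Severity is minor. Events are likely to be rare, the sponsor is consulted, and the numerical effect is one subject at a time in descriptive tables. The frequencies rest on assumed Grade 3 rates of 0.5% to 3%; the only observed figure is 0 of 29, on monotherapy. A reader might infer that the primary endpoint is at risk, but nothing here bears on how ORR or the gating probabilities are calculated. The reason to act is that a participant-safety rule should give one answer.

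**What to change.** Choose one rule and state it in both sections.

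**Preferred**, because 6.4.4 already states it twice: replace the Level 3 paragraph in 6.6.1 with: *After an infusion-related reaction of Level 3 or 4, CS1001 is permanently discontinued (6.4.4); whether BLU-554 continues is decided by the investigator after consulting the sponsor.* Limit the Table 9 Level 3/4 sentence on continuing study treatment to BLU-554.

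**Alternative**, if the sponsor intends re-dosing after Level 3: write it as an explicit exception in both 6.4.4 bullets, require written sponsor approval, and replace the one-hour minimum in 6.6.1 with an infusion rate of no more than 50% of the previous rate.

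**Cost:** one paragraph and one table sentence in the next amendment, or for the alternative two bullets in 6.4.4 plus the timing condition in 6.6.1. Data collection, sample size and analysis do not change.

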6.6.2. Severe Hypersensitivity Reactions and Flu-Like Symptoms

In the event of hypersensitive reactions, the best available medical treatment must be taken for these subjects. It is recommended that subjects should immediately report any delayed response to the investigator.

In the event of generalized allergic reactions/anaphylactoid reactions (typical manifestations occur within a few minutes after dosing and are characterized by respiratory distress, laryngeal edema and/or intense bronchial spasm; subsequent vascular collapse or shock in general but without previous dyspnea; skin manifestations such as itching and urticaria, with/without edema; and gastrointestinal symptoms such as nausea, vomiting, abdominal cramps and diarrhea), the infusion must be discontinued and the subject should discontinue study drug administration.

In the event of hypersensitive reactions, the subject will be given infusions of adrenaline and dexamethasone, followed by immediate monitoring, and the ICU should be prepared for a ready-to-use state when needing to be transferred to the ICU.

If the subject appears the above reactions after receiving the treatment for the first time, it is advisable to administer prophylactic 25 mg indomethacin or a similar dose of NSAIDs (NSAIDs) (e.g., 600 mg ibuprofen and 500 mg naproxen sodium) within 30 to 60 minutes prior to each **subsequent** CS1001 infusion. Or according to the investigator's judgment, other fever treatment may be given to the subject (e.g., paracetamol).

6.6.3. Immune-Related Adverse Events

If an immune-mediated AE is suspected, the investigator should ensure that the evidence of etiology is conclusive or other causes may be excluded.

For any irAE of  $\geq$  Grade 3 or irAE of Grade 2 with the requirement of drug suspension or permanent withdrawal, the investigator should inform the sponsor as soon as possible and consult with the sponsor if necessary.

Based on the severity of AE, CS1001 will be suspended and corresponding treatment will be given. For subjects who use corticosteroids, corticosteroid dose will be gradually reduced within at least 1 month after the adverse reaction is improved to grade 1 or better. Short-term immunosuppressive agents such as tumor necrosis factor antagonists, mycophenolate mofetil or other drugs may be used if needed. If the severity of AE is maintained at grade 1 or better, CS1001 treatment can be restarted. In the event of an immune-mediated persistent, worsening or recurrent adverse event of Grade 3, or an immune- mediated event of Grade 4, CS1001 treatment should be discontinued permanently. For the identification, diagnosis, management and dose adjustment of irAE, please refer to APPENDIX 3: GUIDANCE FOR IMMUNE-RELATED ADVERSE REACTIONS MANAGEMEMT

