# 14.3. APPENDIX 3: GUIDANCE FOR IMMUNE-RELATED ADVERSE REACTIONS MANAGEMEMT

Identification, diagnosis, management of immune-related adverse events and dose adjustment method are listed in detail as following:

irAE	Potential signs and symptoms	Diagnosis and differential diagnosis	Recommended management	Dose modification
Pneumonitis	Symptomatic : dyspnea, cough, pleuritic chest pain, hypoxia Asymptomati c: lung infiltrates that mimic severe bacterial pneumonia	
 
Radiographic imaging of chest
 
Observe the specimen of tissues and lavage fluids used in bronchoscopy to investigate infectious pathogens and perform a pathologic evaluations on them
 
	Moderate (Grade 2): administration of corticosteroids at a dose of 1-2 mg/kg/day prednisone equivalents Severe (≥ Grade 3): high dose corticosteroids (2-4 mg/kg/day IV methylprednisolone) along with antibiotics; in-patient hospitalization; consultation with a respiratory physician; additional immunosuppression with infliximab can be considered	Withhold the administration of CS10 until resolved to ≤ Grade 1 Permanent discontinuation from the study
Colitis	Watery diarrhea, mucus or blood in stool, abdominal pain, nausea/vomiti ng, dehydration, peritoneal signs, bowel perforation	
 
Stool cultures
 
Endoscopy or colonoscopy to rule out infection
 
Biopsy to rule out alternative etiology
 
	Moderate (≤Grade 2) diarrhea: antidiarrheal medication, oral hydration, electrolyte supplement Persistent Moderate (Grade 2) diarrhea: administration of corticosteroids at a dose of 1-2 mg/kg/day prednisone equivalents Severe (Grade 3) diarrhea: high dose corticosteroids (2-4 mg/kg/day IV methylprednisolone) along with antibiotics; infliximab can be	Continue dosing Withhold the administration of CS1001 until resolved to $\leq$ Grade 1 Withhold the administration of CS1001 until resolved to $\leq$ Grade 1

Recurrent severe (Grade 3) or life- threatening (Grade 4): high dose corticosteroids (2-4 mg/kg/day IV methylprednisolone)		considered for steroid refractory diarrhea
high dose corticosteroids (2-4 mg/kg/day IV	discontinuation	
corticosteroids (2-4 mg/kg/day IV	from the study	threatening (Grade 4):
mg/kg/day IV		high dose
		corticosteroids (2-4
methylprednisolone)		mg/kg/day IV
along with antibiotics;		methylprednisolone)

irAE	Potential signs	Diagnosis and	Recommended	Dose modification
	and symptoms	differential	management	
		diagnosis	8	
			infliximab can be	

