			considered for steroid	
			refractory diarrhea; in-	
			patient hospitalization	
			If bowel perforation is	Permanent
			suspected, steroid	discontinuation
			should be withheld,	from the study
			and surgical opinion	
			should be explored; in-	
			patient hospitalization;	
			Infliximab should not	
TT /'/'			be administered	W7.41.11.4
Hepatitis	Symptomatic:	Chemistry:	• Grade 2:	Withhold the
	fever, fatigue,	elevated levels	administration of	administration of
	nausea,	of hepatic transaminases	corticosteroids at a dose of 1-2	CS1001 until
	abdominal pain,			resolved to ≤ Grade 1
	hepatomegaly, Asymptomatic:	• Serologic	mg/kg/day	Glade I
	elevation of liver	testing: should	prednisone equivalents	
	function tests	be performed to rule out viral	-	
	(hepatic	hepatitis	• For subjects with liver metastasis or	
	transaminases,	(including	HCC who entered	
	bilirubin)	hepatitis A and	the study with	
		B),	Grade 2 elevation	
		cytomegaloviru	of AST/ALT,	
		s, and Epstein-	investigational	
		Barr virus	drug will be	
		Ultrasonograms	withheld if	
		of the liver	AST/ALT	
		Biopsy or	increase $\geq 50\%$	
		radiologic	relative to	
			baseline.	

1 1	imaging to		0 0 1	Democrat
		•	Severe ( $\geq$ Grade	Permanent
	distinguish		3): administration	discontinuation
	from other		of high dose	from the study
	etiologies of		corticosteroids (2-	
	hepatic injury,		4 mg/kg/day IV	
	such as		methylprednisolon	
	neoplastic		e); if not improved	
	disease		after 48-72 hours,	
	progression in		alternative	
	the liver,		immunosuppressi	
	infections, and		on agents	
	effects of other		(mycophenolate	
	medications or		mofetil) should be	
	alcohol intake		considered; in-	
			patient	
			hospitalization;	
			consultation with	
			a hepatologist	
		•	For subjects with	
			liver metastasis or	
			HCC who entered	

irAE	Potential signs	Diagnosis and	Recommended	Dose modification
	and symptoms	differential	management	
		diagnosis		
			the study with	
			Grade 2 elevation	
			of AST/ALT,	
			investigational	
			drug will be	
			permanently	
			discontinued if	
			AST/ALT	
			increase $\geq 50\%$	
			relative to	
			baseline and	
			lasting $\geq 1$ week	
			Total serum	
			bilirubin >3 times	
			upper limit of	
			normal	
Hypophysitis	Headache	Clinical	Grade 2 without	Withhold the
	refractory to	chemistry tests	adrenal crisis: high-	administration of
	nonsteroidal	• Endocrinologic laboratory test,	dose corticosteroids	CS1001 until
	anti-	ACTH, thyroid	(methylprednisolone 1	resolved to $\leq$

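### For some brief first Grade 3 immune-related hepatitis events, the protocol body allows CS1001 to restart while the Appendix 3 hepatitis row requires a permanent stop, and no text says which prevails

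*Protocol*

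**What the plan says.** **Protocol 6.6.3.** CS1001 is suspended according to severity. Where steroids are used, "corticosteroid dose will be gradually reduced within at least 1 month after the adverse reaction is improved to grade 1 or better". Then: "If the severity of AE is maintained at grade 1 or better, CS1001 treatment can be restarted". A permanent stop is mandatory "In the event of an immune-mediated persistent, worsening or recurrent adverse event of Grade 3" and for any Grade 4 immune-mediated event. For Grade ≥3 immune-related events, and for Grade 2 events needing suspension or withdrawal, "the investigator should inform the sponsor as soon as possible and consult with the sponsor if necessary". The section ends with a referral: "For the identification, diagnosis, management and dose adjustment of irAE, please refer to APPENDIX 3".

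**Protocol 6.4.2 to 6.4.4.** Drug-related AST, ALT or bilirubin elevation of Grade ≥2 already suspends CS1001 (6.4.2). Dosing may resume after recovery to Grade ≤1 or baseline within 9 weeks (6.4.3). Under 6.4.4, a non-skin Grade 3 drug-related event leads to a permanent stop if it lasts more than 7 days. Grade 3 laboratory abnormalities do not, unless a listed limit is met. The liver limits are AST/ALT >5-10 x ULN for 2 weeks, AST/ALT >10 x ULN, total bilirubin >5 x ULN, or AST/ALT >3 x ULN together with bilirubin >2 x ULN.

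**Protocol Appendix 3 (14.3).** The lead-in reads: "Identification, diagnosis, management of immune-related adverse events and dose adjustment method are listed in detail as following". In the hepatitis row, the line beginning "Severe ( $\geq$ Grade" 3 carries permanent discontinuation as its action, with no condition attached. A separate line covers subjects who entered with Grade 2 AST/ALT: permanent stop if the values rise ≥50% from baseline for ≥1 week.

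**The concern.** Take a subject with a first Grade 3 immune-related hepatitis that settles quickly. A site working from 6.6.3 and 6.4.3 could rechallenge with CS1001. A site working from the Appendix 3 hepatitis row would stop for good. The two sites would treat the same event differently, and the first would re-expose a subject whom the appendix bars.

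The liver is where these rules are likely to be used. Entry allows AST/ALT up to 5 x ULN (5.2). Drug-related ALT and AST increases were reported in 33% and 29% of subjects on BLU-554 alone (2.4.1.1). ALT and AST increases each occurred in 24.1% on CS1001 alone (2.4.1.2). These are all-grade figures and not rates of immune hepatitis, but they mean that sites will often have to classify a liver event and choose a rule.

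**Working it through.** The plan gives no figure to reproduce. The check sets the rules side by side for a first immune-related hepatitis.

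| Event | 6.6.3 | 6.4.3 / 6.4.4 | Appendix 3 hepatitis row |
|---|---|---|---|
| A. Grade 3 clinical event, ≤7 days, no liver limit met, resolves to Grade ≤1 | Restart allowed | Restart allowed | Permanent stop |
| B. Laboratory Grade 3, AST/ALT >5-10 x ULN for <2 weeks, no other limit met, resolves | Restart allowed | Restart allowed | Permanent stop |
| C. Grade 3 clinical event >7 days, or any 6.4.4 liver limit met | Stop if persistent, a term left undefined | Permanent stop | Permanent stop |
| D. Grade 4 | Permanent stop | Permanent stop | Permanent stop |

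The rules part in rows A and B. In row C, 6.4.4 and Appendix 3 agree, even if the event later resolves. Row B assumes that AST/ALT >5-10 x ULN counts as Grade 3. The documents do not reproduce the CTCAE v5.0 cut-offs, so the exact overlap cannot be fixed from them.

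**Minimum duration before a permanent stop.** None in Appendix 3; more than 7 days for a Grade 3 event in 6.4.4; 2 weeks for AST/ALT >5-10 x ULN in 6.4.4; no number in 6.6.3.

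**Is the missing condition in the hepatitis line meaningful?** The Appendix 3 colitis row withholds CS1001 for a first Grade 3 diarrhea and stops it permanently for recurrent Grade 3. The appendix therefore states a recurrence condition where one is intended. The Grade ≥3 hepatitis line has none.

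**Could rechallenge happen in time?** The 9-week window in 6.4.3 (9 x 7 = 63 days) concerns resolution of the event, which rows A and B would normally meet. Adding the steroid taper, taken at its minimum of 1 month (30 days, assumed), leaves 63 - 30 = 33 days for recovery to Grade ≤1, counted from the missed dose with onset on or before it. Recovery by day 14 would end the taper at 14 + 30 = 44 days, with 63 - 44 = 19 to spare. A longer taper uses up that margin, though 6.4.4 lets the sponsor's medical monitor approve delays beyond 9 weeks for steroid tapers.

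**How often?** In CS1001-101 Phase Ia (30 November 2018 cut-off, 2.4.1.2), all immune-related events in 29 subjects were Grade 1 or 2, so 0/29 were Grade ≥3. One-sided 95% upper limit: 1 - 0.05^(1/29) = 0.098. Applied to 40 Phase II subjects: 40 x 0.098 = 3.9. With the optional 15 extra FGF19 IHC+ subjects: 55 x 0.098 = 5.4. Section 4.2.2, at an earlier cut-off of the same study, gives Grades 1-3 but lists no hepatitis, so the count for Grade ≥3 immune hepatitis is 0 on either account.

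**The case against.** The strongest reply is that the protocol does route the reader. Section 6.6.3 closes by sending dose adjustment of immune-related events to Appendix 3, and the appendix says the method is listed there in detail. That is a general rule followed by an organ-specific table, and the table is the natural place to look. This stands in part. A reader might infer that the protocol gives no steer at all, and that would be wrong. But a referral is not a precedence clause. It directly follows a looser restart rule in the same section. The appendix is titled as guidance, the 6.4.1 footnote only suggests considering it, and the general discontinuation criteria in 5.6.1 point to 6.4.4.

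Second, 6.6.3 is permissive. It says when CS1001 must stop and that it can otherwise restart. It does not say that Grade 3 stops only in the listed cases. A site that stops under Appendix 3 breaches no sentence of 6.6.3. A reader might infer two mandatory instructions that cannot both be obeyed, and the text does not support that. What remains is that 6.6.3 permits what the appendix forbids.

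Third, a reader might infer that every resolving first Grade 3 hepatitis is affected. It is not: 6.4.4 independently stops the longer or more marked events (row C).

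Fourth, the sponsor must be told of every Grade ≥3 immune-related event. This is a real safeguard, but consultation is only as needed, and the sponsor would face the same unreconciled texts.

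**Conclusion.** The inconsistency is real but narrow. It concerns rechallenge with CS1001 after a first, short, moderate Grade 3 immune-related hepatitis. Dosing is already suspended at that point, so the question is only whether it may resume. The likely number of subjects is small: about 0 to 4 of 40, as a rough guide. That range rests on monotherapy data in mixed advanced tumors and covers all Grade ≥3 immune-related events, of which hepatitis is a part. The rate for the combination in HCC is not given and could be higher.

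Two further inferences should be resisted. A reader might see competing bilirubin limits, >5 x ULN in 6.4.4 against "bilirubin >3 times" the upper limit of normal in Appendix 3. The table is broken in the text available and the scope of that line cannot be established, so no conflict is claimed. Nor do the documents support any consequence for ORR, the go/no-go gating or the sample size.

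**What to change.** Add one exception in two places, to the restart sentence of 6.6.3 and to the exceptions in 6.4.3: *except immune-related hepatitis of Grade ≥3, for which CS1001 is permanently discontinued as stated in Appendix 3; the 6.4.4 LFT stopping criteria continue to apply.*

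Leave the 6.6.3 sentence on persistent, worsening or recurrent Grade 3 and on Grade 4 events as it is. Replacing it with a general deferral to Appendix 3 would remove the explicit stop for recurrent Grade 3 dermatitis: the dermatitis row only withholds at Grade 3, and the 6.4.4 duration rule excludes skin events. Keeping the wording specific to hepatitis also leaves the colitis row and the 6.4.4 endocrinopathy exception unaltered. Do not extend the rule to events where an immune cause merely cannot be excluded. With transaminase rises this frequent on BLU-554, that would be a change of design and not a clarification.

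The cost is a wording amendment. Phase Ib recruitment is complete (4.3.1), so it applies to Phase II enrolment and to anyone still receiving CS1001. The clinical price is that a few subjects with brief Grade 3 immune hepatitis lose the option of rechallenge. No analysis changes.
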